9.1 Site Labs - See SOE, on page 19, for complete labs schedule

Blood Pressure - sitting

Urinalysis with sediment

Urine: protein, Urine: creatinine on spot sample; Urine protein/creatinine ratio (calculation)

Serum Creatinine

9.2 Central Labs: Mechanistics (See SOE, on page 19, for complete Central Labs schedule)

9.2.1 Anti-HLA antibody: recipient's serum will be tested for the presence of anti-HLA antibodies through Luminex single antigen bead assay. In this assay, patient's serum is incubated with microbeads coated with purified HLA proteins and then a fluorescent anti-IgG is used for antibody detection. Mean fluorescence intensity and donor-specificity of the antibodies present will be determined by correlating with known HLA antigens from donor.

9.2.2 Urine B7-1 quantitative: we will isolate RNA from urinary extracellular vesicles (EVs) of transplanted patients and detect B7-1 mRNA using "Droplet Digital" PCR system.

9.2.3 B7-1 biopsy staining: Using a goat anti-human B7-1 (CD80) antibody, we will perform immunostaining for B7-1 on frozen sections of allograft biopsies.

10. Safety and Reporting:

10.1 Data Safety and Monitoring Board (DSMB)

A Data and Safety Monitoring Board (DSMB) will act in an advisory capacity to the Principal Investigator of this study, to monitor participant safety, data quality and evaluate the progress of the study. The Chair of the DSMB will also act as the study's Medical Monitor (MM). Please see the DSMB Charter, starting on Page 17 of this Protocol.

10.2 Definitions

10.2.1 Adverse Event (AE):

An AE is any *unfavorable* medical occurrence in a human subject enrolled in this study regardless of its causal relationship to study treatment. This may include:

- Abnormal sign (e.g. finding on physical exam or laboratory finding);
- Symptom;
- Disease.

10.2.2 Serious Adverse Event (SAE):

An SAE is an adverse event which meets *any* of the following criteria:

- Results in death;
- Is life threatening (places subject in immediate risk of death from the event as it occurred);
- Requires patient hospitalization or prolongation of existing hospitalization;
- Results in a persistent or significant disability/incapacity;
- Results in a congenital anomaly/birth defect;

- Any clinically significant event that based on the judgment of the Investigator may jeopardize the subject's health and may require medical or surgical intervention to prevent one of the outcomes listed above.

10.3 Reporting Requirements

10.3.1 Adverse Event Reporting Requirements:

Adverse events should be reported on an ongoing basis in the appropriate eCRF in StudyTRAX.

Study sites should follow their IRB guidelines for reporting these events and document in their Study Binders.

10.3.2 Serious Adverse Event Reporting Requirements:

Serious Adverse Events should be reported to the sponsor within 5 working days/7 calendar days of the date that the Study Investigator becomes aware of the event. Please report in the appropriate eCRF AND complete and scan Adverse Event Form (AEF) found in the Manual of Procedures (MOP). Please send the scanned Adverse Event Form to the following email address:

[contact].

Study sites should follow their IRB guidelines for reporting these events and document in their Study Binders.

10.3.3 Non-SAEs Reporting Requirements:

The following are not considered SAEs for this study, however they should still be documented in the subject binder and eCRF when appropriate (i.e. surgical procedure, adverse event):

- a visit to the emergency room or other hospital department < 24 hours, that does not result in admission (unless considered an important medical or life-threatening event);
- elective surgery, planned prior to signing consent;
- admissions as per protocol for a planned medical/surgical procedure;
- routine health assessment requiring admission for baseline/trending of health status (e.g., routine colonoscopy);
- medical/surgical admission other than to remedy ill health and planned prior to entry into the study. Appropriate documentation is required in these cases;
- admission encountered for another life circumstance that carries no bearing on health status and requires no medical/surgical intervention (e.g., lack of housing, economic inadequacy, caregiver respite, family circumstances, administrative reason).

10.4 IND Safety Reporting Requirements:

Per 21 CFR 312.32(c)(1)(i), the Sponsor ([name]) will notify the FDA, Medical Monitor (MM)/DSMB Chair, Partners Human Research Committee (PHRC), BMS (drug manufacturer), and all participating investigators in an IND Safety Report when an event meets ALL of the following criteria:

- suspected adverse reaction (reasonable possibility of relationship to study drug)
- serious
- unexpected

Fatal or life-threatening events will be reported as soon as possible, but no later than 7 days of occurrence.

Serious and unexpected events will be reported as soon as possible, but no later than 15 days of occurrence.

Study sites should follow their IRB guidelines for reporting these events and document in their Study Binders.

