8.2.3.2 Re-Supply

Drug re-supply request form should be submitted electronically or by fax at least 5 business days before the expected delivery date. Deliveries will be made Tuesday through Friday. When assessing need for resupply, institutions should keep in mind the number of vials used per treatment dose, and that shipments may take 14 business days from [BMS or other third-party vendor] receipt of request. Drug is not patient specific. Be sure to check with your pharmacy regarding existing investigational stock to assure optimal use of drug on hand.

9. Study assessments and procedures [Please see: Schedule of Events (SOE) on page 19]:

9A. Belatacept Infusions

See SOE, on page 19, for complete Belatacept infusion schedule.

9A.1 Belatacept Infusion reactions**

In the event of new, serious, and unexpected toxicity potentially related to Belatacept, study drug administration should be interrupted. The investigator must immediately notify the medical monitor (MM). The subject will be considered eligible to receive further study drug treatment only after discussion with the medical monitor.

9B. Early Withdrawal of Study Drug Regimen – safety follow-up schedule:

Subjects in whom Belatacept dosing is discontinued should be placed on a conventional immunosuppressive regimen. To ensure the safety of immunosuppression conversion, repeated blood work for creatinine and drug levels will be performed a 1 week, 2 weeks and 4 weeks post-conversion. A safety follow-up clinic visit 1 month post-conversion will be scheduled.

9C. Study Stopping Rules

Subjects MUST discontinue investigational product (and non-investigational product at the discretion of the investigator) for any of the following reasons:

- Withdrawal of informed consent (subject's decision to withdraw for any reason)
- Any clinical adverse event (AE); abnormal laboratory test results such as refractory neutropenia after immunosuppression adjustment (absolute neutrophil count below 500), refractory life-threatening infection; occurrence of PTLD; refractory acute cellular rejection confirmed by kidney biopsy; or intercurrent illness which, in the opinion of the investigator, indicates that continued participation in the study is not in the best interest of the subject
- Pregnancy
- Loss of ability to freely provide consent through imprisonment or involuntary incarceration for

- treatment of either a psychiatric or physical (e.g., infectious disease) illness

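### For fatal or life-threatening suspected, serious and unexpected events, the outer reporting limits in Sections 10.3.2 and 10.4 are not aligned

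*Combined protocol and SAP*

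**What the plan says.** All references are to the combined protocol and SAP.

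- **Site to sponsor (10.3.2).** "Serious Adverse Events should be reported to the sponsor within 5 working days/7 calendar days of the date that the Study Investigator becomes aware". The section covers every SAE. The definition in 10.2.2 includes any event that "Results in death" and any life-threatening event, and the visible text gives neither a shorter limit.
- **Sponsor onward (10.4).** When an event is a suspected adverse reaction, serious and unexpected, the sponsor notifies five recipient groups: the FDA, the medical monitor/DSMB Chair, the Partners Human Research Committee, the manufacturer and all participating investigators. For the gravest class, "Fatal or life-threatening events will be reported as soon as possible, but no later than 7 days of occurrence". For the rest, "Serious and unexpected events will be reported as soon as possible, but no later than 15 days of occurrence".
- **Medical monitor (9A.1).** Under the heading on infusion reactions: "In the event of new, serious, and unexpected toxicity potentially related to Belatacept, study drug administration should be interrupted". The investigator must notify the medical monitor at once. Under 10.1 the medical monitor is the DSMB Chair.
- **Other channels.** Section 10.3.1 has adverse events entered in the eCRF on an ongoing basis. Section 10.5 requires the Adverse Event Form to be sent within 24 hours of discovering a pregnancy.

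**The concern.** The sponsor cannot report an event that it has not yet heard about. The site's clock in 10.3.2 starts at awareness and the sponsor's clock in 10.4 starts at occurrence, which is the same day or earlier. Both run to 7 days. A site that follows 10.3.2 exactly can therefore use up or overrun the sponsor's whole period for the most serious events. The sponsor also needs some of that time to judge relatedness and expectedness and to prepare the report.

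What is at stake is late notice, measured against the protocol's own commitment, to the 10.4 recipients. They include the other investigators, who may be treating further subjects with the same drug. By contrast, a pregnancy must reach the sponsor within 24 hours, while a drug-related death may take 7 days.

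**Working it through.** **Inputs.** Site limit: 5 working days/7 calendar days from awareness (10.3.2). Sponsor limits: 7 and 15 days from occurrence (10.4). L = days from occurrence to awareness; the documents do not give it, and 0 to 2 is assumed. S = calendar days from awareness to the site's report.

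**Formula.** Days left to the sponsor = (sponsor's limit) - L - S. Both clocks must be counted the same way:

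- Exclusive (start day is day 0): the 7-day limit falls 7 days after occurrence, so days left = 7 - L - S.
- Inclusive (start day is day 1): the limit falls 6 days after occurrence, so days left = 6 - L - S.

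**Site at 7 calendar days.** Exclusive: 7 - L - 7 = -L. Inclusive: 6 - L - 6 = -L. For L = 0, 1, 2 the sponsor has 0, -1, -2 days on either convention.

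**Site at 5 working days, no public holiday.**

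| Day of awareness | S, exclusive | 7 - L - S | S, inclusive | 6 - L - S |
|---|---|---|---|---|
| Monday | 7 | -L | 4 | 2 - L |
| Tuesday to Friday | 7 | -L | 6 | -L |
| Saturday | 6 | 1 - L | 6 | -L |
| Sunday | 5 | 2 - L | 5 | 1 - L |

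The most favourable cell is 2 - L, which is 2, 1, 0 for L = 0, 1, 2. From L = 3 every cell is negative. One public holiday in the window stretches 5 working days to 8 to 10 calendar days (exclusive counting), which leaves -1 to -3 days at L = 0.

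**15-day class, site at 7 calendar days.** Exclusive: 15 - L - 7 = 8 - L. Inclusive: 14 - L - 6 = 8 - L. For L = 0, 1, 2 this is 8, 7, 6 days, so there is no clash at short lags.

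**With a 24-hour first notice (S = 1).** Exclusive: 7 - L - 1 = 6 - L, or 6, 5, 4 days for L = 0, 1, 2. Inclusive counting of the sponsor's limit gives 6 - L - 1 = 5 - L.

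**Limit of any site deadline.** Even with S = 0 the sponsor has 7 - L days. If awareness comes more than 7 days after occurrence, 10.4 is missed whatever the site does. A shorter site deadline therefore does not remove the difference in clock starts.

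**The case against.** **The limits are maxima on different parties.** Both are met whenever the site reports early, and 10.4 also asks for reporting as soon as possible. At zero lag and 7 calendar days they coincide, and some weekdays leave 1 or 2 days. This stands. A reader might infer that the two sections are strictly incompatible, but the documents do not support that: compliance with both is possible, only not guaranteed. The request for speed in 10.4 binds the sponsor, and 10.3.2 has no matching words for the site.

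**Other channels exist.** The medical monitor is available around the clock and is told at once under 9A.1. Adverse events go into the eCRF as they arise. The DSMB may hold an emergency meeting, and the principal investigator, who is also the sponsor, attends open sessions where SAE listings may be shown. In practice these may bring the news sooner. None of them is a timed event report to the sponsor. The Charter's timed links to the principal investigator are a recommendation within 2 weeks of a meeting and immediate notice of a termination decision. In 10.4 the notice runs from sponsor to medical monitor, not the other way.

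**The unseen Manual of Procedures may hold a faster clock.** This cannot be excluded. Section 10.7 also cites a Section 10.9 for SAE reporting, although visible numbering ends at 10.8. As 10.6 sends overdose SAEs to 10.3.2, the 10.9 citation may simply be out of date.

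**Few events qualify.** They must be related, unexpected, and fatal or life-threatening, and Section 8.1 already lists rejection, PTLD, malignancy and serious infection as known risks. This stands. Lag may also be negligible at the sponsor's own hospital. The visible text does not list the three sites, so no count of exposed subjects is offered.

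**Conclusion.** The point holds as a misalignment of outer limits, confined to the 7-day class. With the site at its 7-calendar-day limit, the sponsor has -L days left: none at zero lag, and a missed limit at any lag of 1 day or more. The 5-working-day reading softens this to at most 2 - L days if no public holiday intervenes. The result rests on the assumed lag, on counting both clocks alike, and on no faster rule standing in the Manual of Procedures.

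Two stronger readings are not supported. A reader might infer a breach of the federal regulation that 10.4 cites. Its text is not in the documents, so the lateness shown is only against 10.4's own wording. A reader might also infer that the affected subject goes unprotected. Section 9A.1 interrupts study drug and adds: "The subject will be considered eligible to receive further study drug treatment only after discussion with the medical monitor". Its place under the infusion-reaction heading leaves its scope unclear, but the exposure shown here is late onward notice, not absence of any safeguard.

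**What to change.** Reconcile the three sections:

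1. In 10.3.2, add a first notice from site to sponsor for fatal or life-threatening SAEs, short enough for the sponsor to meet 10.4. One example is the 24-hour Adverse Event Form notice already used in 10.5, with full eCRF completion to follow.
2. In 9A.1, have the sponsor informed at the same time as the medical monitor.
3. Reconcile the clock starts (awareness in 10.3.2, occurrence in 10.4) and say how days are counted. Without this, late awareness alone can defeat 10.4.

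If the Manual of Procedures already sets a faster clock, cite it in 10.3.2. Correct or explain the reference to Section 10.9 at the same time.

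The cost is wording in these sections and a memo to sites. The downside is a small added site burden: an earlier first notice, on an existing form, for a few events in a 36-subject trial. No analysis, endpoint or treatment rule changes.

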10.5 Pregnancy

If, following initiation of the study drug, it is subsequently discovered that a study subject is pregnant or

may have been pregnant at the time of study exposure, including during at least 5 half-lives after product administration, the investigator must immediately notify [name] of this event and complete and send an Adverse Event Form (AEF) to [name] within 24 hours of discovery by investigator. [[name] will then report this AEF to BMS (drug manufacturer) within 24 hours of his knowledge of this event.]

In most cases, the study drug will be permanently discontinued in an appropriate manner (e.g., dose tapering if necessary for subject safety).

In the rare event that the benefit of continuing study drug is thought to outweigh the risk, the Sponsor will consult with BMS representative, and the pregnant subject may continue study drug after a thorough discussion of benefits and risk with the subject

Protocol-required procedures for study discontinuation and follow-up must be performed on the subject unless contraindicated by pregnancy (e.g., x-ray studies). Other appropriate pregnancy follow-up procedures should be considered if indicated.

Follow-up information regarding the course of the pregnancy, including perinatal and neonatal outcome and, where applicable, offspring information must be reported on the Adverse Event Form.

Any pregnancy that occurs in a female partner of a male study participant should be reported to the Sponsor within 24 hours of discovery by investigator. Information on this pregnancy will be collected on the Adverse Events Form (AEF).

Please send the completed and scanned Adverse Event Form to all of the following email addresses: [contact].

[[name] will then report this AEF to BMS (drug manufacturer) within 24 hours of his knowledge of this event.]

10.6 Overdose

All occurrences of overdose must be reported as SAEs (see Section 10.3.2 for reporting details).

An overdose is defined as the accidental or intentional administration of any dose of a product that is considered both excessive and medically important. All occurrences of overdose must be reported as an SAE (see Section 10.3.2 for reporting details.).

10.7 Potential Drug Induced Liver Injury (DILI)

Specific criteria for identifying potential DILI have not been identified for this protocol. Standard medical practice in identifying and monitoring hepatic issues should be followed.

Wherever possible, timely confirmation of initial liver-related laboratory abnormalities should occur prior to the reporting of a potential DILI event. All occurrences of potential DILIs, meeting the defined criteria, must be reported as SAEs (see Section 10.9 for reporting details).

Potential drug induced liver injury is defined as:

1. AT (ALT or AST) elevation > 3 times upper limit of normal (ULN),
AND
2. Total bilirubin > 2 times ULN, without initial findings of cholestasis (elevated serum alkaline phosphatase),
AND
3. No other immediately apparent possible causes of AT elevation and hyperbilirubinemia, including, but not limited to, viral hepatitis, pre-existing chronic or acute liver disease, or the administration of other drug(s) known to be hepatotoxic.

Wherever possible, timely confirmation of initial liver-related laboratory abnormalities should occur prior to the reporting of a potential DILI event. All occurrences of potential DILIs, meeting the defined criteria, must be reported as SAEs (see Section 10.9 for reporting details).

Potential drug induced liver injury is defined as: [can be defined based on specific study]

10.8 Data Monitoring Committee, Data and Protocol Compliance Monitoring, and Other External Committees Please see MOP for information, including how often a site must complete their electronic clinical research forms (eCRFs), query resolution guidelines, regulatory binder requirements, and how the study data, and protocol compliance, will be monitored by the Sponsor ([name]/designated study managers).

11. Statistics: This is a phase I clinical trial to test the safety and gain further insight to the potential effect of Belatacept in proteinuric patients. We plan to recruit 36 patients, based on the feasibility for recruitment in 3 transplant centers and prior literature on recommended sample sizes in Phase I trials.

The primary endpoint of the study will be a 25% reduction in proteinuria from baseline to 12 months. This endpoint was extrapolated from studies with ACE inhibitors showing significant benefit in patients with kidney disease and proteinuria that reached this endpoint (12). For comparison, we will also have a historical control group with patients that fit the inclusion criteria and were managed as standard of practice on our institution. A logistic regression model will be used to control for key variables such as baseline ACEI/ARB use, level of proteinuria, age and gender.

For the primary endpoint: Percentage of those patients who have a $\geq 25\%$ reduction in proteinuria from baseline to 12 months will be reported separately for each group. We will compare these percentages between the two groups using Fisher's exact test. In addition, means and standard deviations of the actual reduction will be reported separately for each group and will be compared between the two groups using a non-parametric test (Wilcoxon rank-sum). These results will also be compared to historical controls. A logistic regression model will be used to control for key variables such as baseline ACEI/ARB use, level of proteinuria, age and gender.

For the secondary endpoints: Descriptive statistics (means, standard deviations and/or percentages) will be reported on percent change of renal function from baseline to 12 months; donor-specific anti-HLA antibodies presence and intensity (MFI); adverse events; acute rejection episodes; blood pressure control; new onset diabetes; and hyperlipidemia. Spearman correlations will be calculated between B7-1 positivity on immunofluorescence on biopsy with B7-1-expression in urine extracellular vesicles. Kaplan-Meyer plots will be used to study graft survival and patient survival and a proportional hazards model will be used here to compare survival between treated and historical controls, controlling for the baseline covariates above.

References:

2. Halimi J-M. Low-grade proteinuria and microalbuminuria in renal transplantation. *Transplantation*. 2013;96(2):121-30.

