7.5 LESS EFFECTIVE METHODS OF CONTRACEPTION

- Diaphragm with spermicide

- Cervical cap with spermicide
- Vaginal sponge
- Male Condom without spermicide
- Progestin only pills by WOCBP subject or male subject's WOCBP partner
- Female Condom*.

* A male and female condom must not be used together

8. Study Drug: Belatacept (Treatment with Belatacept will continue for 12 months)**:

Belatacept conversion dosing: 5 mg/kg IV on days 1, 15, 29, 43 and 57, followed by an infusion every 28 days thereafter. Calcineurin inhibitors (CNI) Taper: CNI dose will remain the same for week 1 and then will be tapered by 25% each week and discontinued at the end of week 4 (day 29).

Infusion pre-medications: none

Duration of Infusion: 30 minutes

Observation period post-infusion: none

Standard of Care (SOC) Dosing of Belatacept:

5 x the patient's weight (in kg) = mg of Belatacept. Dose then needs to be rounded to the nearest 12.5 mg increment. Example: 74 kg patient x 5 = 370 mg; rounded to the nearest 12.5 mg increment = 375 mg. At the end of 12 months, study subjects have completed the study drug protocol and they have the option to continue on Belatacept treatment, paid for by their medical insurance, or they can switch back to a CNI.

**Please see additional important study drug information on pages 11-12.

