Study Visits	Screening	Day 1 60 days	Day 15 + 5 days	Day 29 M 1 + 5 days	Day 43 M 2 + 5 days	Day 57 M 3 + 5 days	Day 85 M 4 + 5 days	Day 113 M 5 + 5 days	Day 141 M 6 + 5 days	Day 169 M 7 + 5 days	Day 197 M 8 + 5 days	Day 225 M 9 + 5 days	Day 253 M 10 + 5 days	Day 281 M 11 + 5 days	Day 309 M 12 + 5 days	Day 337 M 13 + 5 days	M18 + 5 days	
Procedures																		
Full Medical History	X																	
Physical Exam	X																	
Vital Signs^a	X	X	X	X	X	X	X	X	X	X	X	X	X	X	X	X		
Chart Review Only																X	X ^f	
Serum or Urine Pregnancy Test (WOCBP only*)	X*																	
EBV Serology^a	X																	
Spot Urine Protein/ Creatinine Ratio^a	X			X			X			X			X			X		
Urine^{a,b}	X			X			X			X			X			X		
Cholesterol Panel^a	X															X		
Serum Glucose^a	X			X			X			X			X			X		
Serum Creatinine^a	X			X			X			X			X			X		
anti-HLA Antibody^c	X ^a															X		
B7-1 biopsy staining^c	X																	
Research Urine^c	X															X		
Research Blood^c	X															X		
Belatacept Infusions^a		X	X	X	X	X	X	X	X	X	X	X	X	X	X	X		
CNI Taper		X ^d	X ^d	X ^e														
AE/SAE Reporting		X	X	X	X	X	X	X	X	X	X	X	X	X	X	X		

KEY:

^aStandard of Care (SOC)

^bUrine = urinalysis w/sediment **AND** Spot Urine = Urine:Creatinine & Urine:Protein; **AND** Urine Protein/Creatinine ratio = calculation needed

^cCentral Lab = send to BWH (transplant research center, [name])

^dCNI dosing to be tapered 25% of baseline dose **PER WEEK** (weekly reduction NOT represented on this SOE), dates of reduction must be documented in eCRFs.

^eLast day of CNI; CNI completely stopped after this day.

^fCollect information about last blood pressure, medications, serum creatinine and urine protein/creatinine

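### Section 11 analyses only the 12-month value of five scheduled post-baseline protein/creatinine ratios, and compares the continuous reduction without baseline adjustment; a baseline-adjusted two-visit summary would be more precise at little cost

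*Combined protocol and SAP*

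**What the plan says.** Section 11 (Statistics) sets the endpoint: "The primary endpoint of the study will be a 25% reduction in proteinuria from baseline to 12 months". For the responder percentages it says: "We will compare these percentages between the two groups using Fisher's exact test". For the continuous result, "means and standard deviations of the actual reduction will be reported separately for each group", and the two groups are compared by a Wilcoxon rank-sum test with no covariate. Covariates appear only for the binary outcome: "A logistic regression model will be used to control for key variables such as baseline ACEI/ARB use, level of proteinuria, age and gender". The two groups are not named in that sentence. I read them as B7-1 positive and B7-1 negative, because historical controls are mentioned separately.

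In the Schedule of Events, the row "Spot Urine Protein/ Creatinine Ratio^a" is marked at screening and, by column position, at Days 29, 85, 169, 253 and 337. The last of these columns is headed "Day 337 M 13 + 5 days". The column labelled M 12 (Day 309) has no ratio, so I take Day 337 as the 12-month value. A further ratio is collected by chart review at Month 18, after the study treatment period.

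The sample size of 36 rests on feasibility and pilot-size literature. No standard deviation, correlation, alpha or power is given.

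**The concern.** A spot UPCR is a variable measurement and the trial has 36 patients. In the stated analysis each patient contributes one difference between two single samples. Four further on-treatment ratios that the schedule already calls for enter no analysis in Section 11. The plan accepts baseline proteinuria as a covariate, but applies it only to the dichotomised outcome and not to the continuous one.

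What is at stake is precision, above all in the B7-1 comparison, where one group may be small. Section 3 reports 15 of 123 indication biopsies positive (12%), which would be about 4 of 36 patients. It also reports 4 of 8 nephrotic patients positive, which would be up to 18 of 36.

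A second exposure is missing data. Section 11 has no rule for a missing 12-month value, and the early-withdrawal follow-up in Section 9B names creatinine and drug levels but not UPCR. A patient without the final sample may drop out of the proteinuria analysis despite having earlier values.

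**Working it through.** **Plan's own figure.** There is no power or precision calculation to reproduce. The 36 agrees with 12 patients x 3 centres and with 2 per month x 18 months.

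**Inputs.** Visit days come from the Schedule of Events. Everything else is assumed: log UPCR, equal variance at each visit (set to 1), and correlation r between baseline and Day 337 of 0.5 to 0.8. Two correlation structures are used:
- constant: every pair of visits has correlation r;
- autoregressive decay: visits d days apart have correlation r^(d/337).

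**Between-group comparison, variance per patient, groups with similar baselines.**

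| Summary | Formula | r = 0.5 | r = 0.8 |
|---|---|---|---|
| Unadjusted change at Day 337 | 2(1 - r) | 1.00 | 0.40 |
| Day 337, baseline-adjusted | 1 - r² | 0.75 | 0.36 |
| Mean of Days 253 and 337, baseline-adjusted, constant | (1 + r)/2 - r² | 0.50 | 0.26 |
| The same, decay | (1 + r^(84/337))/2 - [(r^(253/337) + r)/2]² | 0.62 | 0.30 |

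For the decay row at r = 0.5: (1 + 0.841)/2 - [(0.594 + 0.5)/2]² = 0.921 - 0.299 = 0.62. At r = 0.8: (1 + 0.946)/2 - [(0.846 + 0.8)/2]² = 0.973 - 0.677 = 0.296.

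Variance saved relative to the unadjusted change:
- Day 337 with baseline adjustment: 1 - 0.75/1.00 = 25%, down to 1 - 0.36/0.40 = 10%.
- Two-visit mean, constant: 1 - 0.50/1.00 = 50%, down to 1 - 0.26/0.40 = 35%.
- Two-visit mean, decay: 1 - 0.62/1.00 = 38%, down to 1 - 0.296/0.40 = 26%.

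Standard errors move less. For the two-visit mean the saving is 1 - √0.50 = 29% to 1 - √0.65 = 19% (constant), and 1 - √0.62 = 21% to 1 - √0.74 = 14% (decay). For Day 337 alone it is 13% to 5%.

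**Single-arm change in all treated patients.** In one arm, the baseline-adjusted mean evaluated at the mean baseline, minus that mean baseline, is the mean change itself. The covariate therefore adds nothing, and only averaging helps.
- Constant: (1 + r)/2 + 1 - 2r = 1.5(1 - r), against 2(1 - r). That is 0.75 against 1.00, and 0.30 against 0.40: a 25% saving at every r.
- Decay: 0.921 + 1 - 1.094 = 0.83 against 1.00 (17%), and 0.973 + 1 - 1.646 = 0.327 against 0.40 (18%).

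**Scope.** These formulas compare means of log UPCR. They do not evaluate Fisher's test, the logistic model or the rank-sum test itself.

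**The case against.** The strongest reply is that a 12-month responder percentage with a simple continuous companion is legitimate for a self-described Phase I study whose size was set by feasibility. That stands, and it is why the point is one of efficiency.

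Second, much of the gain comes from moving the target from one visit to a window. This also stands: if the target stays at Day 337, the saving is 10-25%, and with complete data the earlier visits add essentially nothing. The move is modest, though. Day 29, the last day of CNI under Section 8, is not in the averaged window.

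Third, the groups are not randomised. Section 3 suggests that B7-1 positivity goes with heavier proteinuria, so baselines may differ. Adjusted and change-score analyses can then estimate different quantities, and imbalance raises the variance of the adjusted one. The 1 g/day entry threshold also strains the equal-variance assumption. Both are real limits on the figures.

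Fourth, no UPCR schedule is given for historical controls, so that comparison may gain little.

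A reader might infer that the primary analysis throws away a third to a half of its precision, or that 36 patients could be made to work like 55 to 72 (36/0.65 and 36/0.50). The documents do not support this. They give no correlation, and the range is a variance saving for one type of contrast under constant correlation. Under decay the equivalents are 49 to 58 (36/0.74 and 36/0.62), and for the single-arm change 48 at most (36/0.75). The primary responder analysis is not what these figures measure, and its logistic model already adjusts for level of proteinuria.

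**Conclusion.** The point holds as an efficiency improvement. Five post-baseline ratios are scheduled, Section 11 uses only the 12-month one, and the continuous comparison lacks the baseline adjustment that the plan already accepts for the binary outcome.

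The size depends on the contrast and on assumed correlations. For a between-group comparison, mainly B7-1 positive against negative, the two-visit adjusted mean saves 26-50% of variance across the two structures; baseline adjustment at Day 337 alone saves 10-25%. For the treated-arm change the saving is 17-25%, all of it from averaging. All of this assumes log UPCR, equal variances, similar baselines and r between 0.5 and 0.8. No stated figure in the plan is wrong.

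**What to change.** Keep the 25% responder percentage and Fisher's test as the primary endpoint. Add to Section 11, as the main continuous result, a linear mixed model of log UPCR over the scheduled post-baseline visits, with log baseline UPCR as covariate. From it report:
- the adjusted geometric-mean ratio between B7-1 groups, averaged over Days 253 and 337, with 95% CI;
- the geometric-mean ratio to baseline for all treated patients over the same two visits.

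Give two sensitivity analyses: the Day 337 value alone, and the unadjusted change. Because the groups are not randomised, show the adjusted and unadjusted results side by side. State in the text which visit is the 12-month value.

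The cost is SAP wording and a little analysis time; no new samples are needed. The mixed model also uses the earlier values of patients whose last ratio is missing, provided the missingness is explained by the data already observed. The downsides are these:
- the estimate describes roughly Days 253 to 337 rather than one visit;
- with perhaps four B7-1 positive patients the by-group estimate will stay imprecise, and a simple covariance structure should be named in advance as a fallback;
- historical controls may lack a matching second ratio, in which case that comparison should stay on the 12-month value.
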